4.6.1. Extent of Exposure

Duration of exposure to study drug during the double-blind treatment period will be summarized by treatment arm and provided as listing. Duration of exposure on treatment will be calculated as the date of last dose of study drug (or date of discontinuation) minus the date of first dose of study drug plus 1 day. Total patient-years (PYs) of exposure will be reported for each treatment group for overall duration of exposure. Descriptive statistics (n, mean, SD, minimum, maximum, first quartile, median, third quartile, and maximum) will be provided for patient-days of exposure and the frequency of patient falling into different exposure ranges will be summarized. Exposure ranges are as follows:

- $>0, \ge 12$ weeks, ≥ 24 weeks, and ≥ 60 weeks
- >0 to <12 weeks, ≥12 weeks to <24 weeks, ≥24 weeks to <60 weeks, and ≥60 weeks

Overall exposure will be summarized in total PYs, which will be calculated as follows:

Exposure in patient years = $Sum \ of \ duration \ of \ exposure$ (for all patients in treatment arm) / 365.25.

No inferential analysis for comparison between treatment arms will be performed.

4.6.2. Adverse Events

AEs are recorded in the eCRF. Each AE will be coded to System Organ Class (SOC) and Preferred Term (PT), using the *Medical Dictionary for Regulatory Activities* (MedDRA) version that is current at the time of database lock. Severity of AEs is recorded as mild, moderate, or severe.

A treatment-emergent adverse event (TEAE) is defined as an event that first occurred or worsened in severity after baseline and on or prior to the earliest of the visit study drug disposition dates or the last visit date during the treatment period, whichever occurred first, and up to 50 days after study treatment discontinuation. Baseline for Period 2 is defined as all preexisting conditions recorded at Visit 1 and any AEs recorded before the first dose of study intervention. Baselines for other periods are defined as unresolved AEs just prior to the first dose of each period. The MedDRA Lowest Level Term (LLT) will be used in defining which events

are treatment-emergent. The maximum severity for each LLT will be used as baseline. If an event is preexisting during the baseline period for Period 2, but it has missing severity, and the event persists during the treatment period or up to 50 days after treatment discontinuation, then the baseline severity will be considered mild for determining any postbaseline treatment-emergence (that is, the event is treatment-emergent unless the severity is coded mild at postbaseline). If an event occurring postbaseline has a missing severity rating, then the event is considered treatment-emergent. Should there be insufficient data for an AE start date to make this comparison (for example, the AE start year is the same as the treatment start year, but the AE start month and day are missing), the AE will be considered treatment-emergent. For events occurring on the day of the first dose of study treatment, Week 0 (V2) in most cases, the events will be assumed to occur posttreatment and considered as TEAE. For events occurring on the day of doses except for the first dose of study treatment, the events will be considered to occur prior to the study drug injection.

In general, summaries will include the number of patients in the safety population (N), frequency of patients experiencing the event (n), and relative frequency (that is, percentage; n/N*100).

In an AE overview table, the number and percentage of patients in the safety analysis set who experienced death, a serious adverse event (SAE), any TEAE, permanent discontinuation from study drug due to an AE, or a severe TEAE will be summarized by treatment group.

The number and percentage of patients with TEAEs will be summarized by treatment group in 2 formats listed below. For events that are gender specific, the denominator and computation of the percentage will only include patients from the given gender.

- By MedDRA PT nested within SOC with SOCs ordered alphabetically, and events ordered within each SOC by decreasing frequency in the 1000 mg of peresolimab Q4W treatment group
- By MedDRA PT with events ordered by decreasing frequency in the 1000 mg of peresolimab Q4W treatment group

AEs leading to permanent discontinuation of study drug and AEs leading to temporary interruption of study drug will also be summarized by treatment group using MedDRA PT nested within SOC. AE leading to temporary interruption of study drug will be identified using the response of "Drug Interrupted" in the question "What action taken with study treatment?" on the *Adverse Event* eCRF. Events will be ordered by decreasing frequency within SOC in 1000 mg of peresolimab Q4W treatment group.

A summary of temporary interruptions of study drug due to AEs will also be provided, showing the number of patients who experienced at least 1 temporary interruption and the number of temporary interruptions per patient with an interruption. Further, the duration of each temporary interruption (in days) and the cumulative duration of dose interruption (in days) using basic descriptive statistics (n, mean, SD, minimum, first quartile, median, third quartile, and maximum) will be displayed. Duration of study drug interruption will be calculated as: visit date of the missed dose – date of next resumed dose + 1, only if both dates are provided.

The number and percentage of patients with TEAEs will be summarized by maximum severity, SOC and PT by treatment using MedDRA PT ordered by decreasing frequency for the TEAEs. For each patient and TEAE, the maximum severity for the MedDRA level being displayed is the maximum postbaseline severity observed from all associated LLTs mapping to that MedDRA PT.

Adverse events of special interest include hypersensitivity, injection site reactions, infections, and malignancy.

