5.5. Criteria for Temporarily Delaying Enrollment of a Participant

This section is not applicable for this study. All entry criteria must be met within the specified visit intervals in the SoA.

6. Study Intervention(s) and Concomitant Therapy

Study intervention is defined as any investigational intervention(s), marketed product(s), placebo, or medical device(s) intended to be administered to/used by a study participant according to the study protocol.

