9.3.5. Safety Analyses

Safety analyses will be assessed by evaluating exposure, AEs, laboratory analytes, vital signs, and adverse events of special interests.

Duration of exposure to therapy during the treatment periods will be calculated for each participant and summarized by treatment group.

The AEs will be coded according to the MedDRA and summarized by system organ class, preferred term, severity, and relationship to the study intervention. All AEs, including preexisting conditions, will be listed by participant, visit, preferred term, treatment group, severity, and relationship to the treatment.

A TEAE is defined as an event that first occurred or worsened in severity after baseline, with baseline defined as all pre-existing conditions recorded at Visit 1 and any AEs recorded before the first dose of study intervention (that is, during the interval between Visits 1 and 2, and recorded with the time of onset before the first dose of study intervention). The treatment period will be used as the postbaseline period for the analysis. For events that are gender specific, the denominator and computation of the percentage will include only participants from the given gender.

The number and percentage of participants who reported TEAEs, TEAEs by maximum severity, deaths, SAEs, TEAEs related to study intervention, discontinuations from the treatment due to an AE, and adverse events of special interests will be summarized. TEAEs (all, by maximum severity), SAEs including deaths, and AEs that lead to treatment discontinuation will be summarized and analyzed by MedDRA system organ class and preferred term.

Treatment-related TEAEs (TEAEs related to study intervention) are defined as events that are indicated by the investigator on the CRF to be related to treatment.

Adverse events of special interest or special safety topics will be identified by a standardized MedDRA query or a Lilly-defined MedDRA preferred term listing.

Follow-up emergent AEs, SAEs including deaths, and AEs that lead to study discontinuation will be summarized. All AEs, including pre-existing conditions, will be listed by participant, visit, preferred term, treatment group, severity, and relationship to the treatment.

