Section 4.6.2	• Added definitions of baseline for Period 2 and other periods.	Baseline definition will be different between Period 2 and other periods.
	Added additional condition for TEAE. AEs occurring on the	AE data do not include time of onset.

	date of first injection are considered as TEAE. AEs occurring on date of other injections are considered as post-injection except for the first injection date. • Removed paragraph for	To avoid redundancy due to the
	common TEAEs with ≥1%.	sample size per treatment group.
	Added definition of AESI.	• Clarification
Section 4.6.2.2	Removed "Event maps to PT of Infusion related reaction"	Not relevant to the trial.
Section 4.6.2.4	• Removed analyses for infections categorized Grampositive/negative bacterial infection, mixed aerobicanaerobic bacterial infection, fungal infections, viral infections, other infections, and opportunistic infections as assessed by the investigator.	• Not relevant to the trial.
Section 4.6.2.4		• Clarification
	Added analyses plan for herpes simplex.	Clinical request
Section 4.6.2.5	Added SMQ for malignancies	• Clarification
Section 4.6.2.6	Added SMQ for depression	• Clarification
Section 4.6.3	Added categorization for shifts of hepatic measures, hematology, lipid effects, and renal function.	• Clarification
Section 4.6.4.4	Added definitions for immunogenicity analysis	• Clarification
		• Not informative analysis given the sample size
Section 4.7.4	Added analysis plan for Japanese subgroup analysis	To prepare Japanese submission.
Appendix 4	Added definition of handling missing data for preexisting conditions and medical history	Clarification

Appendix 5	Added definition of handling	Clarification
	missing data for prior and	
	concomitant medication	
Appendix 10	Added list of PTs for herpes	• To provide a full list of PTs.
	zoster, herpes simplex, and	
	hepatitis B virus	
Appendix 11	Added definition of grade for	To provide categorization for shift
	hematologic events, lipid	tables.
	effects, and renal function	

Statistical Analysis Plan (SAP) Version 3 based on the protocol dated 31 May 2023 was approved prior to the final database lock and includes the following changes. Minor corrections/additions may not be included.

Section	Description of Change	Change Rationale	
Section 1.2 & 4.1	• Replaced "early termination" to "early discontinuation", and "ET" to "ED"	To use the consistent terminology as per study protocol.	

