1.2. Study Design

Study KDAF is a Phase 2b, randomized, double-blind, placebo-controlled study to determine the appropriate dose and dosing frequency of peresolimab in adult participants with moderately-to-severely active RA.

[figure not shown]
This study includes a

- Period 1: screening period occurring approximately 1 to 42 days prior to Period 2
- Period 2: 12-week double-blind, placebo-controlled treatment period
- Period 3: 48-week double-blind treatment period, and
- Period 4: posttreatment follow-up period occurring 4 and 12 weeks from last treatment period visit (Week 60) or Early Discontinuation Visit.

See the Schedule of Activities (SoA) in the protocol for visit schedule, procedural and assessment details.

In the remainder of this statistical analysis plan (SAP), the first 12 weeks in Period 3 (that is, Weeks 12 to 24) will be referred as Period 3A and the last 36 weeks in Period 3 (that is, Weeks 24 to 60) as Period 3B for an analysis purpose. Combined Periods 2 and 3 will be referred as the Treatment Period (Weeks 0 to 60).

Figure KDAF.1.1 describes the study design for the treatment periods (Periods 2 and 3).

[figure not shown]

Abbreviations: CDAI = Clinical Disease Activity Index; SC = subcutaneous injection; Q4W = every 4 weeks; Q12W = every 12 weeks.

Note: At Week 12, participants receiving placebo Q4W will begin receiving either 400 mg or 1000 mg peresolimab Q4W. At Week 24, participants receiving 400 mg or 1000 mg peresolimab Q4W may be switched to Q12W dosing following assessment of CDAI scores.

Figure KDAF.1.1 Study design.

Participant population

Treatment period design

- 100 mg of peresolimab every 4 weeks (Q4W)
- 400 mg of peresolimab Q4W
- 1000 mg of peresolimab Q4W
- placebo Q4W up to Week 12 followed by 400 mg of peresolimab Q4W, and
- placebo Q4W up to Week 12 followed by 1000 mg of peresolimab Q4W.

Participants randomly assigned to placebo Q4W at Week 0

At Week 12, participants receiving placebo Q4W will begin receiving either 400 mg or 1000 mg peresolimab Q4W based on randomization at Week 0. Treatment assignment will be blinded, and the participants will continue their assigned peresolimab dose and dosing frequency until the end of the study.

Participants randomly assigned to 100 mg peresolimab at Week 0

Participants receiving 100 mg peresolimab will continue their assigned dose and dosing frequency throughout the duration of the treatment period. No changes will occur.

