4.1. General Considerations

Statistical analysis of this study will be the responsibility of sponsor or its designee. A detailed SAP describing the statistical methodologies will be developed by the sponsor or its designee.

Handling of missing, unused, and spurious data are addressed prospectively in the overall statistical methods described in the protocol and in the SAP, where appropriate. Adjustments to the planned analyses are described in the final clinical study report (CSR).

Baseline for the Treatment Period is defined as the last nonmissing assessment on or prior to the date of the first injection of study treatment for efficacy, unless otherwise specified. In most cases, this will be the measure recorded at Week 0 (Visit 2). For safety analyses, baseline will be defined by period as last nonmissing assessment prior to the first dosing of each period. The Treatment Period starts after the first injection and ends on date of Visit 18 (Week 60) or early discontinuation (ED). Any assessment collected after the first injection is defined as postbaseline for the Treatment Period. If ET visit does not occur, last injection date will be considered as the end of the treatment period. Baseline for safety analysis of the Posttreatment Follow-Up period (Period 4) is defined as the last nonmissing assessment prior to entering Period 4, that is date of Visit 18 (Week 60) or ET.

During this study, data issue was identified for the collection date/time of the electronic clinical outcome assessments (eCOA). Same analysis visit was assigned to eCOA assessment with different collection date than the corresponding visit date. Because of this, study team came up with a method to handle this data issue, which is the analysis visit numbers for electronic clinical outcome assessments (eCOA) data will be assigned based on the actual visit date recorded in the electronic case report form (eCRF). If the eCOA assessment date is within +/- 3 days window of the actual visit, then the analysis visit number of the eCOA assessment will be assigned as the actual visit number. If the eCOA assessment date is outside +/- 3 days window of all the actual visits, then the analysis visit of the eCOA assessment will be considered as unscheduled visit. The eCOA data will be used for the analysis only when the analysis visit number of the eCOA assessment is identical to the visit number captured in the eCOA system.

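### An adverse event dated on a placebo participant's first peresolimab day (Week 12) is deemed pre-injection, so by inference it counts under placebo in the Period 2 tables

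*SAP*

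**What the plan says.** SAP Section 4.6.2 has two conventions for adverse events dated on a dosing day. On the day of the first dose of study treatment, which it identifies as Week 0 in most cases, the event is taken as post-treatment and treatment-emergent. On all other dosing days, "except for the first dose of study treatment, the events will be considered to occur prior to the study drug injection".

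The same section sets the adverse event baseline after Period 2: "Baselines for other periods are defined as unresolved AEs just prior to the first dose of each period". SAP Section 4.1 is consistent with this: "For safety analyses, baseline will be defined by period as last nonmissing assessment prior to the first dosing of each period".

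SAP Section 1.2 places the switch: "At Week 12, participants receiving placebo Q4W will begin receiving either 400 mg or 1000 mg peresolimab Q4W". It also states that "the first 12 weeks in Period 3 (that is, Weeks 12 to 24) will be referred as Period 3A". Table KDAF.3.1 (footnote a) and Section 4.1 pool both placebo sequences into one placebo group for Period 2. Section 4.6 summarizes safety descriptively by treatment group and by period.

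The opening of Protocol Section 6 makes placebo a study intervention: "Study intervention is defined as any investigational intervention(s), marketed product(s), placebo, or medical device(s) intended to be administered".

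Protocol Section 9.3.5 words its baseline in terms of events "recorded with the time of onset before the first dose of study intervention". The SAP's Version History gives the reason for the day convention: "AE data do not include time of onset".

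**The concern.** The exemption follows the first dose of study treatment, not the first dose of peresolimab. In the three peresolimab arms these are the same day. In the two placebo sequences they are 12 weeks apart, and the day of first exposure to the drug gets the pre-injection convention.

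Period 2 is the only placebo-controlled period. A reaction that followed a first peresolimab injection could be tabulated as a placebo event and also be missing from the Period 3A columns for the switch sequences. Without onset times any same-day rule misplaces some events. This one does so at the one boundary where treatment changes in the placebo sequences only, so the error does not cancel between arms.

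**Working it through.** **Tracing one event.** Take a new adverse event dated on the Week 12 injection day in a placebo participant.

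1. Week 12 is not that participant's first dose of study treatment, because placebo was given at Week 0. Reading the phrase as the first dose of each period does not fit: Section 4.6.2 ties it to Week 0, and it says first dose of each period where it means that.
2. The event is therefore deemed to precede the Week 12 injection, which is the first Period 3A dose.
3. If unresolved, it belongs to the Period 3A baseline and is not treatment-emergent under PBO/PER400Q4W or PBO/PER1000Q4W unless it worsens.
4. It is after the Period 2 baseline. The documents state no Period 2 cut-off for counting events, so its place in the pooled Period 2 placebo column is inferred from steps 2 and 3 and the by-period layout.

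**Size.** The plan gives no figure to reproduce and no same-day event rate. Protocol Section 2.2 reports no injection site or infusion reactions in the two Phase 1 studies. All rates below, the 10% dropout and independence between doses are assumptions.

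Let f be the same-day risk at the first peresolimab dose, l at later peresolimab doses, q per placebo dose, and d = 0.10 the dropout before Week 12.

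Participants moved = n × f, with n from 120 × 0.90 = 108 to 120 (placebo size from SAP Section 5):

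| f | n = 108 | n = 120 |
|---|---|---|
| 0% | 0 | 0 |
| 1% | 1.1 | 1.2 |
| 2% | 2.2 | 2.4 |
| 5% | 5.4 | 6.0 |
| 10% | 10.8 | 12.0 |

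Effect on the Period 2 risk difference (RD), with Period 2 doses at Weeks 0, 4 and 8:

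- Benchmark, these three dosing days only: PER = 1 − (1 − f)(1 − l)²; PBO = 1 − (1 − q)³; RD = PER − PBO.
- Current rule, which adds the Week 12 day: PER′ = PER + (1 − d)(1 − PER)l; PBO′ = PBO + (1 − d)(1 − PBO)f.
- Error in RD = −(1 − d)[f × RD + (1 − PER)(f − l)]. If f = l, the fractional loss is (1 − d)f: 0.9%, 1.8%, 4.5% and 9.0% at f = 1%, 2%, 5% and 10%.

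Worked case f = l = 5%, q = 1%: PER = 1 − 0.95³ = 14.26%; PBO = 1 − 0.99³ = 2.97%; RD = 11.29 points. PER′ = 14.26 + 0.9 × 85.74 × 0.05 = 18.12%; PBO′ = 2.97 + 0.9 × 97.03 × 0.05 = 7.34%; RD′ = 10.78 points.

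The last column moves Week 12 events for the placebo sequences only (PER′ − PBO).

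| f / l / q | Benchmark RD | Current rule | Placebo-only change |
|---|---|---|---|
| 5% / 5% / 1% | 11.29 | 10.78 (−0.51) | 15.15 (+3.86) |
| 2% / 2% / 1% | 2.91 | 2.86 (−0.05) | 4.60 (+1.69) |
| 5% / 2% / 1% | 5.79 | 3.07 (−2.72) | 7.43 (+1.64) |
| 2% / 1% / 1% | 0.98 | 0.10 (−0.88) | 1.84 (+0.86) |
| 5% / 0 / 0 (extreme) | 5.00 | 0.50 (−4.50) | 5.00 (0) |

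The loss is small when reactions recur at every dose and large only when they concentrate at the first. A change confined to the placebo sequences inflates the contrast whenever l is above zero, because the peresolimab arms would still count four dosing days against three.

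**The case against.** The strongest reply is about reach.

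- **Inference.** The Period 2 placement is not written down. True, and the missing cut-off is part of what needs correcting. The documented steps still take the event out of Period 3A.
- **Tables already spared.** The events most likely on an injection day, hypersensitivity and injection site reactions, have their own summaries over the Treatment Period (SAP Sections 4.6.2.2 and 4.6.2.3). For that period Table KDAF.3.1 has switch-sequence columns and no placebo-only column. This stands and confines the effect to the by-period adverse event tables. The exposure-adjusted hypersensitivity rates count events while on peresolimab, so they depend on how the first peresolimab day is programmed.
- **Recurrent reactions.** Events on the Week 16 or Week 20 injection day still fall in Period 3A under the switch sequences. This stands too; only events confined to the first peresolimab day are lost there.
- **Assumed rates.** Nothing in the documents supports first-dose concentration, and Protocol Section 2.3.1 reports no apparent trend in any adverse event. The tables are descriptive and all adverse events are listed. These points limit the severity.
- **Direction.** The Version 2 change log describes other injection-day events as post-injection. The current text governs, and the difference is not itself an error. If post-injection was what was programmed, the misplacement does not arise, so the derivation should be confirmed.

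None of this removes the defect: as written, the rule gives a one-directional misattribution at the switch.

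**Conclusion.** The concern holds and should be fixed. As written, the same-day rule treats an adverse event on a placebo participant's first peresolimab day as preceding that injection. By inference it then falls in the pooled Period 2 placebo column. The bias is toward hiding an excess on peresolimab whenever there is one and risk at the first dose is at least as high as later.

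Under the assumed rates and 10% dropout, between 0 and 12 participants' events move. The Period 2 risk difference loses 0.05 to 0.5 points in the equal-risk cases tabulated, and 0.9 to 2.7 points where risk is higher at the first dose and placebo events occur. In the extreme first-dose-only case it falls from 5.0 to 0.5 points. The true effect may be zero. It touches descriptive by-period tables only. Confidence is medium, because the Period 2 placement is inferred and the rates are unknown.

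**What to change.** State in SAP Section 4.6.2 that, in every arm, adverse events with onset or worsening dated on the day of the Week 12 injection are treated as post-dose and counted in Period 3A. Period 2 then takes same-day events from Weeks 0, 4 and 8 in all arms, and a switcher's first-peresolimab-day events count under PBO/PER400Q4W or PBO/PER1000Q4W. Do not apply the change to the placebo sequences alone.

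Also state the Period 2 cut-off for adverse events, say whether the day of the first peresolimab dose counts as time on peresolimab in the exposure-adjusted rates, and confirm which direction was programmed.

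The cost is one or two sentences and one derivation flag applied to all arms. Some events that truly preceded the Week 12 injection will be counted in Period 3A, by the same rule in every arm. If Week 24 keeps its present convention, Period 3A takes same-day events from four dosing days (Weeks 12, 16, 20 and 24). No between-treatment comparison is planned there, so no contrast is biased. If Period 2 tables were already produced at the primary outcome lock, counts may differ from that output, and the clinical study report should explain the change.

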Participants randomly assigned to 400 mg or 1000 mg peresolimab at Week 0

Participants receiving 400 mg or 1000 mg peresolimab will continue their assigned dose and dosing frequency until Week 24. At Week 24, participants may be switched to every 12 weeks (Q12W) dosing following assessment of CDAI scores, unless they received rescue medication prior to Week 24.

Abbreviations: CDAI = Clinical Disease Activity Index; Q4W = every 4 weeks; Q12W = every 12 weeks.

- At Week 24 using the Visit 9 (Week 24) assessments, a participant does not achieve CDAI LDA
 - o These participants will receive permitted rescue therapy.
- For participants that achieved CDAI LDA at Week 24, those who do not maintain CDAI LDA for 2 consecutive visits after Week 24
 - o These participants will receive peresolimab Q4W and permitted rescue therapy.
 - If a participant is currently receiving peresolimab Q4W, they will continue receiving peresolimab Q4W.

• If a participant is currently receiving peresolimab Q12W, they will switch to peresolimab O4W.

[figure not shown]
Escape criteria after Week 24

A participant not achieving ≥20% improvement in both TJC and SJC at 2 consecutive visits after Week 24, while receiving rescue therapy, should be permanently discontinued from study intervention. Participants may continue in the study and receive additional standard of care therapies at the investigator's discretion.

Participation in an open-label extension study

If an open-label extension study is enrolling at the time the participant completes Visit 18 (Week 60), they will be given the opportunity to enroll in that study.

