A listing of patients with detectable hepatitis B virus (HBV) DNA will be provided.

HBV DNA status (not detectable, detectable but not quantifiable [that is, <lower limit of detection (LLOD)], quantifiable [that is, ≥LLOD]) will be summarized, stratified by applicable baseline HBV serology status.

A summary table of herpes zoster will be provided, including event maximum severity, seriousness, whether resulting in temporary study drug interruption, whether resulting in study drug discontinuation, and event outcome. See Appendix 10 (Section 6.10) for PT list for herpes zoster.

A summary table of herpes simplex will be provided, including event maximum severity, seriousness, whether resulting in temporary study drug interruption, whether resulting in study drug discontinuation, and event outcome. See Appendix 10 (Section 6.10) for PT list for herpes simplex.

The time to onset of first treatment-emergent infectious AE during the Treatment Period will be defined as follows:

```
Time to onset of first treatment-emergent infectious AE (in weeks) = (Start\ date\ of\ first\ infectious\ AE - Date\ of\ first\ injection\ +1)/7.
```

Note that if an infectious AE was preexisting prior to the date of first injection and subsequently became treatment-emergent due to worsening post-baseline, the date of worsening will be used in place of the AE start date.

If a patient does not have a treatment-emergent infectious AE during the Treatment Period, they will be censored at the date of completion or ED from the Treatment Period. Kaplan-Meier estimates of the proportion of patients not yet experiencing their first treatment-emergent infectious AE at 12, 24, 36, 48, and 60 weeks will be provided for each treatment arm. A Kaplan-Meier plot of the time to onset will be presented by treatment arm.

The duration of each treatment-emergent infectious AE during the Treatment Period will be defined as follows:

```
Duration of treatment-emergent infectious AE (in weeks) = (End date of AE – Start date of AE + 1) / 7.
```

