4.6.4.4. Immunogenicity

A participant is defined as evaluable for TE ADA if the participant has a nonmissing baseline ADA result and at least 1 nonmissing postbaseline ADA result.

A participant who is evaluable for TE ADA is defined as TE ADA+ if either of the following holds:

A NAb+ participant is defined as a TE ADA+ participant where an NAb Present result is detected for at least 1 postbaseline ADA sample.

The frequency and percentage of TE ADA+ and NAb+ patients will be summarized by treatment arm.

The time to the development of TE ADA will be calculated as:

Time to development of TE ADA (in days) = Date of development of TE ADA – Date of first injection + 1.

If a patient has not developed TE ADA, they will be censored at the date of the last immunogenicity assessment during the Treatment Period.

The frequency and percentage of patients with both a TE ADA+ incidence (yes, no) and at least 1 TE hypersensitivity AE (yes, no) will be summarized by treatment arm. Similarly, the frequency and percentage of patients with both a TE ADA+ incidence (yes, no) and at least 1 treatment-emergent injection site reaction (yes, no) AE will be summarized by treatment arm.

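### The formula for study drug interruption duration in SAP 4.6.2 subtracts the later date from the earlier one, so every gap longer than one day comes out negative

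*SAP*

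**What the plan says.** SAP 4.6.2 (Adverse Events) plans a summary of temporary interruptions of study drug due to adverse events. Besides counts, it will show "the duration of each temporary interruption (in days) and the cumulative duration of dose interruption (in days) using basic descriptive statistics". The calculation follows in the same paragraph: "Duration of study drug interruption will be calculated as: visit date of the missed dose – date of next resumed dose + 1". It applies where the missed-dose visit and the resumption are both dated. The SAP version history lists this calculation among the Version 3 additions and labels it a clarification.

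Elsewhere the SAP builds durations and times to event the other way round, with the later date first:

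- Exposure (SAP 4.6.1): "date of last dose of study drug (or date of discontinuation) minus the date of first dose of study drug plus 1 day".
- Duration of an infectious adverse event, in weeks (SAP 4.6.2.4): "End date of AE – Start date of AE + 1) / 7".
- Time to treatment-emergent anti-drug antibodies (SAP 4.6.4.4): "Date of development of TE ADA – Date of first injection + 1".

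No section reverses the order for interruptions or says that an absolute value is taken.

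**The concern.** The visit at which a dose was missed comes before the date on which dosing resumes. The formula therefore subtracts the later date from the earlier one, and the result falls as the interruption lengthens.

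This is the only definition in the SAP for a planned safety output. Protocol 7.1.1 (liver tests) and 7.1.3 (infections, latent tuberculosis treatment) both provide for withholding study drug, so the summary is likely to have entries. Followed literally, it would report negative means and medians. The minimum and maximum would also swap roles, with the longest interruption appearing as the minimum.

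If a programmer notices the negative values and repairs them without guidance, different repairs give different tables.

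**Working it through.** **Inputs**

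- Formula: SAP 4.6.2, as quoted above.
- Gap g: days from the missed-dose visit to the next resumed dose, with g > 0 for a real interruption.
- Illustrative gaps: the documents report no interruption lengths, so I take gaps from the dosing schedule in SAP 1.2. The arms start on four-weekly dosing, for example "100 mg of peresolimab every 4 weeks (Q4W"), which gives 28 days, and twice that is 56 days. For the 400 mg and 1000 mg arms, "At Week 24, participants may be switched to every 12 weeks (Q12W) dosing following assessment of CDAI scores", which gives 84 days.

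The SAP gives no worked interruption duration, so there is no figure of its own to reproduce.

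**Formulas**

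- As written: missed − resumed + 1 = 1 − g.
- Absolute value of that: g − 1, for g of 1 or more.
- Order reversed, +1 kept (the SAP's convention elsewhere): resumed − missed + 1 = g + 1.
- Order reversed, +1 dropped (elapsed days): g.

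**Results, in days**

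| Gap g | As written | Absolute value | Reversed, +1 | Reversed, no +1 |
|---|---|---|---|---|
| 1 | 0 | 0 | 2 | 1 |
| 2 | −1 | 1 | 3 | 2 |
| 7 | −6 | 6 | 8 | 7 |
| 14 | −13 | 13 | 15 | 14 |
| 28 | −27 | 27 | 29 | 28 |
| 56 | −55 | 55 | 57 | 56 |
| 84 | −83 | 83 | 85 | 84 |

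The formula returns zero at g = 1 and a negative value for every longer gap. It returns a positive value (1) only if dosing resumes on the same date, which is hardly an interruption.

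**Cumulative duration.** Take one participant with two interruptions of 28 and 56 days:

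- As written: −27 + (−55) = −82.
- Reversed with +1: 29 + 57 = 86.
- Reversed without +1: 28 + 56 = 84.
- Absolute values: 27 + 55 = 82.

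**Why the absolute value fails.** Under the order as written, the +1 shortens the magnitude by a day where it should lengthen it. The absolute value is therefore one day below elapsed time and two days below the inclusive count, for each interruption.

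**Effect on the planned statistics.** Because 1 − g is a decreasing linear function of g, the per-interruption mean becomes 1 minus the mean gap. The median behaves in the same way, and the quartiles and extremes change places. The number of interruptions and the per-interruption standard deviation do not change.

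**The case against.** The best defence is that this is an obvious transposition. The output is called a duration in days, the rest of the SAP shows the intended convention, and negative durations would stand out in any review of the tables. The affected results are descriptive, and no inference is planned on them.

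Most of that stands, and it keeps the point small. It does not make the line correct. The sentence says how the value will be calculated and ends in +1, so the dash cannot be read as a range. Nor does spotting the negative sign settle the repair: for a 28-day gap, three plausible repairs give 27, 28 or 29.

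Three stronger readings are tempting and are not supported:

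- **That durations would be wrong for every participant.** The formula applies only to those with an AE-related temporary interruption, identified from the action-taken question on the adverse event form, and only where both dates are recorded. The documents give no interruption rate, so the number affected is unknown.
- **That wider safety results are affected.** The number of participants interrupted, interruptions per participant, events leading to interruption and AE incidence do not use the formula. Exposure is computed from dose or discontinuation dates, without subtracting interruptions.
- **That the +1 is itself a mistake.** It acts in the wrong direction only because the dates are in the wrong order. Once they are reversed, it is the SAP's usual inclusive count.

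**Conclusion.** The formula is wrong as written. It returns 1 − g for a gap of g days: zero at one day and negative beyond that, for example −27 days at 28, −55 at 56 and −83 at 84. Measured against the inclusive count used elsewhere in the SAP, each interruption is understated by 2g days, since (g + 1) − (1 − g) = 2g.

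The consequence is limited to the per-interruption and cumulative duration summaries, in participants with an AE-related interruption and both dates present. Efficacy, the primary endpoint, AE incidence, interruption counts and exposure are untouched.

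The conclusion rests only on the resumed dose coming after the missed one. The 28-, 56- and 84-day gaps are illustrations from the dosing schedule, not observed data. How consecutive missed doses are grouped into one interruption is a separate question, which the SAP leaves unstated and which this conclusion does not depend on.

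**What to change.** In SAP 4.6.2, replace the formula with: date of next resumed dose − visit date of the missed dose + 1, keeping the existing condition that both dates are recorded. This is the smallest change that agrees with SAP 4.6.1, 4.6.2.4 and 4.6.4.4, and it gives 29 for a 28-day gap.

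The inclusive form counts the day of resumption as an interrupted day. If the sponsor would rather report elapsed days without it, drop the +1 and state that choice, so that a 28-day gap gives 28. Either is coherent, but the SAP should name one.

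The cost is one line of SAP text and a check that the program behind the interruption table uses the corrected order. If the SAP is not reopened, the correction can be recorded in the clinical study report, where SAP 4.1 already places adjustments to planned analyses. No data collection changes.
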